7.6.3. Anti-Drug Antibodies

Results of the ADA assay including titers will be listed and the number of subjects with a confirmed positive sample will be summarized. Neutralizing antibody assays results will be listed for positive ADA samples.

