**Table 14: Phase 2 — Blood Sampling for Pharmacokinetic, Pharmacodynamic, Genetic, and Other Assessments**

Visit or Cycle	Day	For PK (see NOTE)	Additional Time Points for Rich PK Subset	For ADA	For PBMC	For [REDACTED]	For PGx
Screening	—	—	—	—	—	—	X 
Cycle 1	1	Predose  30 min ( $\pm$ 15 min) 	—	Predose 	Predose 	Predose 	—
	2	—	24 h ( $\pm$ 60 min) 	—	—	—	—
	8	—	168 h ( $\pm$ 4 h) 	—	—	—	—
Cycle 2	1	Predose 	—	Predose 	Predose 	Predose 	—
Cycle 3	1	Predose 	—	Predose 	Predose 	—	—
Cycle 4	1	Predose  30 min ( $\pm$ 15 min) 	—	Predose 	Predose 	Predose 	—
	2	—	24 h ( $\pm$ 60 min) 	—	—	—	—
	8	—	168 h ( $\pm$ 4 h) 	—	—	—	—
Cycles 5, 6, 12, 18, 24	1	—	—	Predose 	—	—	—
Discontinuation	—	X	—	X	X	X	—
Safety Follow-up Visit	4 wk after last dose	X	—	X	—	—	—
Follow-up Visit	3 mo after last dose	X	—	X	—	—	—

Abbreviations: ADA: antidrug antibody; [REDACTED] DNA: deoxyribonucleic acid; h: hour(s); mo: month; min: minute(s); PBMC: peripheral blood mononuclear cell; PGx: pharmacogenomics(s); PK: pharmacokinetic(s); wk: week(s).

 Blood sample for PGx is collected only if an ‘optional’ PGx consent is signed.

 Predose samples will be collected within 30 minutes before starting the AGEN2034 infusion.

 Blood samples collected on Day 1 at 30 ( $\pm$  15) minutes after the **end** of infusion

 As of Amendment 5 (27 September 2019), additional rich PK sampling will be collected in a subset of approximately 20 subjects in selected sites. Rich PK sampling will occur on Days 2 and 8 of Cycles 1 and 4 at 24 hours ( $\pm$  60 min) and 168 ( $\pm$  4) hours, respectively, after the **start** of the infusion.

**NOTE:** It is important to record all infusion start dates/times, infusion end dates/times, infusion interruption(s) start and end dates/times, infusion flush end dates/times, and blood sample dates/times completely and accurately (to the nearest minute). Blood for the 30-minute postdose PK samples should **never** be taken during the infusion and should be drawn at least 15 min after the end of infusion.

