3. STUDY OBJECTIVES AND ENDPOINTS

3.1. PRIMARY OBJECTIVE OF PHASE 2

- To assess the objective response rate (ORR) according to Response Evaluation Criteria in Solid Tumors (RECIST) 1.1, as determined by an Independent Endpoint Review Committee (IERC)

3.2. SECONDARY OBJECTIVES OF PHASE 2

- To assess the safety and tolerability of balstilimab in subjects with metastatic, locally advanced, and/or unresectable cervical cancer
- To characterize the balstilimab pharmacokinetic (PK) profile
- To evaluate the immunogenicity of balstilimab and correlate it to exposure
- To assess ORR according to RECIST 1.1 as determined by investigator
- To assess duration of response (DOR), disease control rate (DCR), duration of stable disease (SD), time to response, and progression-free survival (PFS) time per RECIST 1.1
- To assess overall survival (OS) rate
- To assess OS time

3.3. EXPLORATORY OBJECTIVES OF PHASE 2

- [REDACTED]
- [REDACTED]

- Baseline expression of programmed death-ligand 1 (PD-L1) association with clinical outcomes

3.4. PRIMARY ENDPOINTS OF PHASE 2

- Confirmed ORR per RECIST 1.1, as determined by an IERC, in the analysis population.

Note: The population for primary efficacy analysis, specified in the study protocol, consists of “All subjects in Phase 2 who have received ≥ 1 dose of trial treatment and have measurable disease at baseline, according to the IERC assessment.”

3.5. SECONDARY ENDPOINTS OF PHASE 2

- Frequency, severity, and duration of treatment-emergent adverse events (TEAEs) and laboratory abnormalities, using NCI-CTCAE v4.03
- Balstilimab PK parameters which may include (but are not limited to) maximum drug concentration observed postdose at steady-state ($C_{\max-ss}$), minimum observed concentration at steady-state ($C_{\min-ss}$), area under the drug concentration-time curve within time span t_1 to t_2 at steady-state ($AUC_{(t_1-t_2)-ss}$), area under the drug concentration-

time curve from time zero to time t ($AUC_{(0-t)}$), area under the drug concentration-time curve from time zero to infinity ($AUC_{(0-\infty)}$), time to maximum observed concentration (t_{max}), terminal disposition rate constant (λ_z), terminal elimination half-life ($t_{1/2}$), systemic clearance (CL), and volume of distribution (Vd)

Note: Analysis of PK parameters and correlation with anti-drug antibody concentrations is not covered in this SAP, it will be conducted according to a separate PK analysis plan.

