6. ANALYSIS SETS

The following analysis sets will be used for analysis of Phase 2 data:

Table 2: Definitions of Analysis Sets

Analysis Set	Definition	Analysis to Be Conducted	Interim Analysis
All subjects analysis set	Includes all subjects who signed informed consent form (ICF), irrespective if they passed or failed screening for Inclusion and Exclusion criteria.	Will be used only for listing of all subjects who signed informed consent who either received study treatment or were excluded from the study during the screening period due to failure to meet eligibility criteria.	All patients who signed informed consent by the cut-off date for data.
Safety (Note: All dosed subjects)			
Safety analysis set (SAS)	Includes all subjects who received ≥ 1 dose of study treatment.	It will be used for safety evaluation, as the primary analysis in the final analysis of data and as a secondary set in any interim analysis.	All patients dosed by the cut-off date for data.
ITT (Note: No exclusions based on information obtained after study treatment initiation)			
ITT efficacy analysis set (ITT EAS)	Includes all subjects who received ≥ 1 dose of study treatment, with measurable disease at baseline (per IERC).	Primary analysis set for efficacy.	All patients with measurable disease at baseline (per IERC) dosed by the cutoff-date for enrollment.

ITT Prior Line of Therapy analysis set (ITT PLT)	Includes all subjects who received ≥ 1 dose of study treatment, with measurable disease at baseline (per IERC), and had prior line of platinum-based treatment in metastatic, persistent or recurrent setting, as determined by Independent Review Committee	Secondary analysis set for efficacy	N/A
Per Protocol (Note: Possible exclusions based on information obtained after study treatment initiation)			
Per Protocol (PP) Efficacy Analysis Set (PP EAS)	Includes all subjects who received ≥ 1 dose of study treatment, had measurable disease at baseline by IERC, and were not excluded due to important protocol deviations.	The PP EAS set will be used for sensitivity analysis of the primary efficacy analysis.	All patients dosed by the cutoff-date for enrollment, had measurable disease at baseline by IERC, and were not excluded due to important protocol deviations (exclusions will be decided case by case).

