6.1. ANALYSIS TO BE CONDUCTED FOR DIFFERENT ANALYSIS SETS

Table 3 below shows analysis sets used for different data omitting All Subjects Analysis Set (as this is only used for listing of screened and enrolled subjects) and PK Analysis Set (as this analysis will be conducted according to a separate PK analysis plan).

Table 3: Applications of Analysis Sets

Analysis	ITT EAS	ITT PLT	PP EAS	SAS
Subject Disposition	2	2		1

Protocol Deviations				1
Demographic and Baseline Characteristics	2	2		1
Medical History				1
Ongoing Medical History				1
Cancer History	1	1		2
Prior Cancer Therapies and Procedures	1	1		
Prior and Concomitant Medications				1
Drug Exposure				1
Adverse Events				1
Anti-Drug Antibodies				1
Clinical Laboratory Tests				1
Body Weight and Vital Signs				1
12-lead ECG				1
Pregnancy tests				1
ORR per RECIST 1.1	1	1	2	
Time to Response	1	1	2	
Duration of Response	1	1	2	
Disease Control Rate	1	1	2	
Tumor Control Rate	1	1	2	
Progression-Free Survival	1	1	2	
Overall Survival	2	2		1

Legend: 1 = Primary Analysis, 2 = Secondary Analysis

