7.2. GENERAL STATISTICAL PROCEDURES

Frequency distributions for categorical variables will be provided as number of subjects in the category and the percentages of the total number of subjects in the given population as noted. Counts of missing observations will be included in the denominator and presented as a separate category. Percentages will be reported to one decimal place.

A 2-sided 95% Wilson score CI for categorical variables without multiplicity adjustment will be provided where appropriate for efficacy analysis.

The descriptive statistics for continuous variables will be number of subjects, mean, standard deviation, median, minimum, and maximum. Mean and median will be reported to 1 more decimal place than the raw data, while the standard deviation will be reported to 2 more decimal places than the raw data. Minimum and maximum will be reported the same as the original data.

Summary tables may be replaced with listings when appropriate. For instance, an AE frequency table may be replaced with a listing if it only contains a few unique preferred terms (PTs) reported on relatively few subjects.

All listings (with the exception of All Subject listings) will be performed using the Safety Analysis Set and sorted by subject ID, ITT EAS, ITT PLT analysis set, and PP EAS membership (first subjects included in these sets) and, if applicable, by visit date unless otherwise specified.

The study drug name will be abbreviated in the tables, listings, and figures (TLFs) as “Bal” for balstilimab (AGEN2034).

Time intervals (in days), unless specified otherwise, will be calculated as difference between ending and start day + 1 day. For conversion to months, interval days will be divided by 30.4375.

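### The SAP's ADA summary uses neither baseline status nor sample timing, so as written it does not isolate antibodies induced by the drug

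*SAP*

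**What the plan says.** Immunogenicity is a Phase 2 secondary objective. SAP 3.2 states it as "To evaluate the immunogenicity of balstilimab and correlate it to exposure".

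SAP 7.6.3 holds the whole ADA analysis in this plan. On individual data, "Results of the ADA assay including titers will be listed". For the summary, "the number of subjects with a confirmed positive sample will be summarized". Neutralizing-antibody results are listed for positive samples. The section names no time point, does not refer to baseline, and has no category for antibodies that appear or rise after dosing.

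Protocol Table 14 schedules ADA samples before dosing on Day 1 of Cycles 1 to 6, 12, 18 and 24, then at discontinuation and at 4 weeks and 3 months after the last dose. Its footnote on timing reads "Predose samples will be collected within 30 minutes before starting the AGEN2034 infusion", so the Cycle 1 Day 1 sample precedes any drug.

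The denominator comes from three other places:
- SAP Table 3 has a single entry for ADA, in the Safety Analysis Set column, marked as primary ("Legend: 1 = Primary Analysis, 2 = Secondary Analysis").
- SAP Table 2 defines that set: "Includes all subjects who received ≥ 1 dose of study treatment". It does not require an ADA sample.
- SAP 7.2 takes percentages as "percentages of the total number of subjects in the given population as noted" and adds: "Counts of missing observations will be included in the denominator and presented as a separate category".

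A note in SAP 3.5 sends PK parameters and their correlation with ADA concentrations to a separate PK plan. It does not mention ADA incidence.

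**The concern.** An immunogenicity summary should tell the reader how many subjects developed antibodies because of the drug. A count of everyone with a positive sample at any time can include reactivity that was there before dosing. A denominator of everyone dosed can include subjects who were never tested after dosing. The first raises the figure and the second lowers it, and the summary alone would not show which effect is larger.

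Elsewhere in the safety section the SAP does use the pre-dose state. Section 7.6.2 separates pre-existing conditions and prior AEs from treatment-emergent ones. Section 7.6.4 uses shifts from baseline grade, and 7.6.5 and 7.6.6 use change from baseline or from pre-dose. ADA has a scheduled pre-drug sample and no comparable rule.

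At stake is the reading of a secondary objective. Under SAP 4.2 the safety part of the BLA Filing analysis covers all dosed subjects, so this count would be among its results.

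**Working it through.** The documents state no human ADA rate and no ADA sample size, so there is no ADA figure of the plan's own to reproduce. The check has a textual part and an illustration.

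**1. How the written rule classifies each kind of subject** (SAP 7.6.3, Tables 2 and 3, and 7.2, against protocol Table 14)

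| Subject | Under the SAP as written | Drug-induced? |
|---|---|---|
| Predose negative, later confirmed positive | Counted | Yes |
| Predose positive only | Counted, since no time limit applies | No |
| Predose positive, later titer rise | Counted, not distinguished | Boosted |
| Only a predose sample, negative | In denominator, not positive, not missing | Unknown |
| No ADA result at all | In denominator, shown as missing (7.2) | Unknown |

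Rows 2 to 4 are the gap. Row 5 is already handled by SAP 7.2.

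**2. Illustration: inputs**
- N = 150, the planned Phase 2 size (SAP 7.1).
- b = share with pre-existing reactivity: assumed 0% to 10%.
- m = share with no post-baseline sample: assumed 0% to 15%.
- t = true treatment-induced rate among baseline-negative subjects with a post-baseline sample: assumed 2%, 5% and 10%.

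Every subject is taken to have a baseline result, and m is taken to be unrelated to baseline status.

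**3. Formula**

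As-written count = N·b + N·(1 − b)·(1 − m)·t

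As-written figure = count / N

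**4. Results at the two extremes**

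| True t | Lowest (b = 0, m = 15%) | Highest (b = 10%, m = 0) |
|---|---|---|
| 2% | 150 × 0.85 × 0.02 = 2.55; 2.55/150 = 1.7% | 15 + 135 × 0.02 = 17.7; 17.7/150 = 11.8% |
| 5% | 150 × 0.85 × 0.05 = 6.375; 6.375/150 = 4.25% (4.2% in the summary figures) | 15 + 135 × 0.05 = 21.75; 21.75/150 = 14.5% |
| 10% | 150 × 0.85 × 0.10 = 12.75; 12.75/150 = 8.5% | 15 + 135 × 0.10 = 28.5; 28.5/150 = 19.0% |

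**5. A middle case: b = 5%, m = 5%, t = 5%**
- As written: 7.5 + 150 × 0.95 × 0.95 × 0.05 = 7.5 + 6.77 = 14.27, and 14.27/150 = 9.5%.
- Treatment-induced among baseline-negative subjects with a post-baseline sample: 6.77/135.4 = 5.0%.
- Treatment-induced among all subjects with both a baseline and a post-baseline result: 6.77/142.5 = 4.75%.

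The last two differ only by the factor 1 − b, so the choice between them matters little as long as it is stated.

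**The case against.** The best reply is that 7.6.3 is brief rather than wrong. It does not name the predose sample as included. SAP 5.1 supplies a baseline definition for all evaluations unless otherwise noted, and SAP 5.5 analyses data by scheduled visit where appropriate. A by-visit ADA table would show Cycle 1 predose separately and would not contradict 7.6.3. Results and titers are listed, so baseline and later positives can be separated subject by subject. All of this stands, and it makes the point a gap in the stated summary and not a flaw in data collection. It does not close the gap: no section supplied says how baseline enters the ADA count, and a listing is not a prespecified classification.

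Some stronger readings are tempting, and the documents do not support them.

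- *The plan deliberately counts predose positives.* This follows only from the absence of a time limit; the text does not say so.
- *Untested subjects are treated as negative.* SAP 7.2 shows missing observations as their own category. Only subjects with a predose sample and nothing later fall outside it. They may be few, since Table 14 schedules draws at discontinuation and after the last dose even for someone dosed once.
- *The reported rate is inflated by a known multiple.* In the illustration the highest ratio is 11.8/2 = 5.9 at a true 2% but 19.0/10 = 1.9 at a true 10%. With no pre-existing reactivity there is no inflation. The ratio is set by the assumed inputs.
- *The SAP commits to a biased incidence rate.* Section 7.6.3 promises a number of subjects; the percentage comes from 7.2 and Table 3.
- *The separate PK plan does not classify ADA status.* That plan was not available for review. The SAP assigns it the exposure correlation and is silent on the rest.

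Restricting the denominator to tested subjects also answers a somewhat different question from the all-dosed count, which is a reason to keep both.

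**Conclusion.** The concern holds as a gap in specification. Applied literally, SAP 7.6.3 counts a subject positive only before drug and leaves a subject with only a predose sample unclassified in the denominator, so the summary does not isolate drug-induced ADA. No supplied document defines treatment-emergent ADA.

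The size cannot be derived from the documents. The ranges in the working rest on the assumed 0% to 10% pre-existing reactivity and 0% to 15% without a post-baseline sample. They show that the as-written figure can lie below or well above the true rate, and they do not predict where this trial will fall.

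This is a minor point on a secondary endpoint. The data needed are already scheduled, and neither the primary ORR analysis nor its sample size depends on it.

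**What to change.** Amend SAP 7.6.3 to report:

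1. Baseline ADA prevalence, using the SAP 5.1 definition of baseline.
2. Treatment-induced ADA: baseline negative with at least one confirmed post-dose positive, among subjects with a baseline and at least one post-dose result.
3. Treatment-boosted ADA, shown separately: baseline positive with a titer rise beyond a threshold. The documents give no assay data from which to set it, so it should be set from the assay's own performance and fixed before the ADA data are reviewed.
4. The number of dosed subjects with no post-dose result, with the present all-dosed count kept alongside.

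The cost is a few lines of SAP text, one more table and a slightly smaller denominator for item 2. No new samples are needed, since Table 14 already schedules the predose draw and 7.6.3 already provides for titers.

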7.6.4. Clinical Laboratory Tests

For clinical laboratory parameters, descriptive summary tables for observed values and changes from baseline will be provided by visit.

Laboratory values will also be categorized according to their NCI-CTCAE v4.03 toxicity grade, for the following parameters: ALT, AST, Bilirubin, Creatinine, Hemoglobin, Platelets, Neutrophils, and Lymphocytes. For applicable parameters, shift tables will be presented from the baseline toxicity grade to the worst post-baseline visit value (scheduled or unscheduled). All test results and associated normal ranges from local laboratories will be reported in SI units. All tests with numeric values will have a unique unit per test. Any laboratory test results and associated normal ranges from local laboratories will be converted to SI units. For the limited number of cases where the associated normal ranges from a local laboratory cannot be obtained despite due diligence, if query is unsuccessful at resolving issue and analysis is mandatory then the clinical scientist and medical monitor can provide a suitable normal range to be used in determining CTC grading and flags for above and below normal and the inferred normal range will be flagged in listings.

If a test value is reported with “<” or “>” sign (as below or above some detection limit), the test value will be imputed in summaries at the limit of detection (that is ignoring “<” or “>” signs), however the measurement will be listed as originally reported.

A standard ‘eDISH’ (evaluation of Drug-Induced Serious Hepatotoxicity) plot will be presented to display on the log-log scale the correlation between peak total bilirubin and alanine aminotransferase (ALT), both in multiples of ULN, with horizontal and vertical lines for Hy’s law thresholds, i.e., $3 \times \text{ULN}$ for ALT and $2 \times \text{ULN}$ for total bilirubin.

Listing will be provided for Safety Analysis Set.

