##### **1.1.3.1. Common Adverse Reactions of Nivolumab**

Adverse reactions observed in more than 20% of subjects treated with nivolumab in clinical trials included (Opdivo® 2015):

- In melanoma: Fatigue, rash, musculoskeletal pain, pruritus, diarrhea, and nausea.
- In metastatic NSCLC: Fatigue, musculoskeletal pain, decreased appetite, cough, and constipation.
- In advanced RCC: Asthenic conditions (decreased activity, fatigue, and malaise), cough, nausea, rash, dyspnea, diarrhea, constipation, decreased appetite, back pain, and arthralgia.
- In cHL: Fatigue, upper respiratory tract infection, pyrexia, diarrhea, and cough.

The most frequent severe or serious reactions, occurring in more than 2% of patients, included:

- In melanoma:
  - Pretreated (n = 268): 2%–5% abdominal pain, hyponatremia, increased aspartate aminotransferase, and increased lipase.

- Untreated (n = 206): 2%–4% gamma-glutamyl transferase (GGT) increase, diarrhea, musculoskeletal pain, increased alanine aminotransferase (ALT), increased aspartate aminotransferase (AST), increased alkaline phosphatase, and increased bilirubin.
- Nivolumab-only arm of combination study (n = 313): 2%–5% diarrhea, increased ALT, increased AST, hyponatremia, increased alkaline phosphatase, anemia, and lymphopenia (4.3%); and increased lipase (9%).
- In NSCLC (n = 287): >2% serious pneumonia, pulmonary embolism, dyspnea, pleural effusion, and respiratory failure.
- In RCC (n = 287): >2% serious acute kidney injury, pleural effusion, pneumonia, diarrhea, and hypercalcemia.
- In cHL (n = 263): >1% serious infusion-related reaction, pneumonia, pleural effusion, pyrexia, rash, and pneumonitis.

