#### **8.3.4.2. Laboratory Variables**

Laboratory results will be classified by grade according to NCI CTCAE. The worst on-trial grades after first trial treatment will be summarized. Shifts in toxicity grading from first treatment to highest grade will be tabulated. Results for variables that are not part of NCI CTCAE will be presented as below, within, or above normal limits. Only subjects with post-baseline laboratory values will be included in these analyses.

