Unless otherwise stated, the number of subjects with an event (subject-wise) and the number of events (event-wise) will be provided for each summary.

Immune-related AEs will be tabulated using investigator-reported irAEs. .

Infusion related AEs will be tabulated using infusion-related reactions as reported by the investigators.

The following summaries by either SOC and PT or by PT and by toxicity grade will be provided. Summaries will be sorted by decreasing incidence of PT (within SOC, if applicable).

- TEAEs by SOC and PT, and by PT
- TEAEs by relationship to study drug, toxicity grade, SOC, and PT
- Drug-related TEAEs by SOC and PT, and by PT
- TEAEs leading to permanent treatment discontinuation by PT
- TEAEs leading to death by PT
- Drug-related TEAEs leading to permanent treatment discontinuation by PT
- Drug-related TEAEs leading to death by PT
- Serious TEAEs by SOC and PT, and by PT
- Serious TEAEs by relationship to study drug and toxicity grade, by SOC and PT
- Drug related serious TEAEs by SOC and PT, and by PT
- irAEs by SOC and PT, and by PT
- irAEs by relationship to study drug, toxicity grade, SOC, and PT
- Infusion-related TEAEs by SOC and PT, and by PT
- Infusion-related TEAEs by relationship to study drug, toxicity grade, SOC, and PT
- Laboratory abnormalities worsening (in at least one on-study measurement, relative to baseline) by NCI-CTCAE v4.03 criteria.
- ALT, AST, or bilirubin normal at baseline but with elevations $\geq 2 \times$ ULN.

The overall summary of will be reported by age (age < 55 vs age ≥ 55 , age < 65 vs age ≥ 65 , and age < 75 vs age ≥ 75), by race group including at least 5 subjects (groups < 5 subjects will be reported summarily as “Other”, patients treated in France who did not report race will be summarized as “Not reported (France)”), region (US vs EU vs other), and by normal vs abnormal creatinine and bilirubin levels at baseline.

In addition, the overall summary of AE incidence per month of drug exposure will be presented. Such a summary will report #patients/(total time of exposure in months) and #AEs/(total time of exposure in months.)

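### SAP 7.6.4 limits CTCAE grading and grade shift tables to 8 laboratory tests and omits the protocol's below/within/above-normal presentation; the change is not declared in SAP 4.1 and its scope is unclear against SAP 7.6.2

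*SAP*

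**What the plan says.** The Phase 2 secondary endpoint (Protocol 2.1.2, SAP 3.5) is the frequency, severity and duration of TEAEs and of laboratory abnormalities by NCI CTCAE v4.03. No laboratory test is singled out or excluded.

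Protocol 8.3.4.2 states: "Laboratory results will be classified by grade according to NCI CTCAE". It then summarizes worst grades after first treatment, tabulates shifts to the highest grade, and adds: "Results for variables that are not part of NCI CTCAE will be presented as below, within, or above normal limits". It gives no list of tests.

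SAP 7.6.4 has three layers:
- For laboratory parameters in general, "descriptive summary tables for observed values and changes from baseline will be provided by visit".
- For grading, values are placed in an NCI-CTCAE v4.03 "toxicity grade, for the following parameters: ALT, AST, Bilirubin, Creatinine, Hemoglobin, Platelets, Neutrophils, and Lymphocytes".
- For shifts, "For applicable parameters, shift tables will be presented from the baseline toxicity grade to the worst post-baseline visit value (scheduled or unscheduled").

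Normal limits otherwise appear mainly in the rule for a reference range that a local laboratory cannot supply. A substitute range may then be used in "determining CTC grading and flags for above and below normal". A listing and an eDISH plot complete the section.

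SAP 7.6.2 includes, among the adverse event outputs, a summary of "Laboratory abnormalities worsening (in at least one on-study measurement, relative to baseline) by NCI-CTCAE v4.03 criteria". It names no tests. SAP 4.1 lists six changes from the protocol's planned analysis; none concerns laboratory data.

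**The concern.** The SAP is the document that will be programmed. Where it names 8 tests, those 8 will be graded and shifted, and a protocol rule that it does not repeat is likely not to be carried out. The endpoint would then be answered in full for a subset of tests, and nobody reading SAP 4.1 would learn that the scope had narrowed.

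The tests left out matter for this drug. Protocol 1.1.2.2 and 2.2 take nivolumab's safety profile as the best guide to AGEN2034. Protocol 1.1.3.2 names thyroid disorders, adrenal insufficiency, hypophysitis and type 1 diabetes among the notable immune-mediated reactions. Protocol 1.1.3.1 names hyponatremia, hypercalcemia and raised alkaline phosphatase among the more frequent severe or serious ones. Protocol Table 8 itself judges TSH against the limits of normal. The tests that bear most directly on these events are outside the SAP 7.6.4 list.

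**Working it through.** There is no sample size or error rate to reproduce. The check compares the sections and counts tests.

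**Count of tests.** Protocol Table 15, leaving out pregnancy tests and the two Phase 1-only autoimmunity tests, has 24 chemistry + 10 hematology + 2 coagulation + 4 endocrine = 40 tests. All 8 tests in SAP 7.6.4 are among them, so 40 − 8 = 32 are outside the grading list. (Table 13 also mentions an absolute eosinophil count and urinalysis, which are not in this count.)

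**Core chemistry.** This is the panel drawn during treatment cycles (Protocol Table 13, footnote 15). It has 13 tests, of which SAP 7.6.4 names 4: ALT, AST, total bilirubin and creatinine. That leaves 13 − 4 = 9: alkaline phosphatase, BUN/urea, calcium, chloride, glucose, magnesium, phosphorus, potassium and sodium.

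**Endocrine tests.** Footnote 19 lists ACTH, FSH (only if applicable), free T4 and TSH. Setting FSH aside, 0 of 3 are in the SAP list.

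**Side by side.**

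| Element | Protocol 8.3.4.2 | SAP 7.6.4 | SAP 7.6.2 |
|---|---|---|---|
| CTCAE grading | Laboratory results, no list | 8 named tests | Worsening from baseline, no list |
| Grade shift table | Yes, no list | Applicable parameters, from baseline grade | Not stated |
| Tests outside CTCAE | Below/within/above normal | No such table | Not covered |

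**Two readings of the worsening summary in SAP 7.6.2.**
- If it is unrestricted, a CTCAE-gradable test outside the 8 has its worsening summarized but gets no baseline-to-worst shift table. The two SAP sections then differ in scope. A test that CTCAE does not grade gets no categorical summary.
- If it follows the 7.6.4 list, all 32 tests have only by-visit statistics and listings, apart from any adverse event that is reported.

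On either reading, 32 tests have no grade shift table in 7.6.4, and tests without a CTCAE grade lose the presentation that the protocol promised.

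**Whether other outputs fill the gap.**
- By-visit tables give n, mean, SD, median, minimum and maximum (SAP 7.2). They do not say how many subjects were abnormal, which is what a frequency endpoint asks, and SAP 5.5 leaves unscheduled values out of them. SAP 5.5 keeps unscheduled values for toxicity grading, but 7.6.4 provides no grading for these tests.
- Listings hold the values but give no frequencies.
- Adverse event tables depend on reporting. Protocol 7.1.2 says that an abnormal laboratory value is not an adverse event unless it comes with signs and symptoms, leads to discontinuation or is judged medically important. The thyroid, pituitary-adrenal and diabetes clusters in SAP 7.6.2 are built from reported preferred terms.

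**The case against.** Several points on the other side are sound.

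First, a reader might infer that the tests outside the list get no severity analysis at all. The documents do not support that. The worsening summary in SAP 7.6.2 cites CTCAE v4.03 as its own criterion, is relative to baseline, and on its wording covers any gradable test. What stands is unclear scope for gradable tests and a missing categorical table for the others.

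Second, a reader might infer that by-visit tables hide extreme values. Minimum and maximum are reported, so extremes at scheduled visits can be seen. The number of subjects affected cannot.

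Third, a reader might multiply the 9% increased-lipase rate in Protocol 1.1.3.1 by 150 subjects to get a count of abnormalities missed. That does not hold. The rate is for severe or serious reactions in the nivolumab-only arm of one melanoma combination study (n = 313), a different drug and tumor. Lipase is also in the full chemistry panel, which Protocol Table 13 marks at screening, discontinuation, the safety visit and the first follow-up visit, and not at treatment-cycle visits. No expected count can be drawn from it.

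Fourth, Protocol 8 lets the SAP modify planned analyses and requires an amendment only for major changes to the primary endpoint or its analysis. A shorter list is therefore permitted. But SAP 4.1 exists to record such changes and goes as far as recording a renamed analysis set, so silence leaves it open whether this was a decision or an oversight.

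Fifth, immune toxicity is also examined through the adverse event clusters, by severity, onset, duration and treatment. That lowers the stakes but does not replace laboratory categories.

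**Conclusion.** The point holds in limited form. SAP 7.6.4 narrows grading and grade shift tables to 8 of the 40 tests counted from Table 15, omits the below/within/above-normal presentation, and does not declare either change. Its scope also needs reconciling with SAP 7.6.2. The consequence is clearest for the 9 of 13 core chemistry tests without a grade shift table in 7.6.4, and for TSH, free T4 and ACTH, which have neither a grade nor a low/normal/high summary there.

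Two assumptions apply. The shift tables for applicable parameters are taken to mean the graded tests, since they start from a baseline grade. The documents do not say which tests CTCAE v4.03 grades, so how the 32 divide between grading and normal-limit categories is unknown. The conclusion does not depend on that division, because the protocol requires one or the other and 7.6.4 provides neither for these tests.

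This is a should-fix on a descriptive secondary safety endpoint. It does not affect the primary endpoint, and collection of the data is not in question.

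**What to change.** In SAP 7.6.4, replace the list of 8 with a rule:
- Apply CTCAE v4.03 grades to every collected test that has them, with baseline-to-worst shift tables using scheduled and unscheduled values.
- Give low/normal/high shift tables, also with unscheduled values, for the remaining tests. Include at least TSH, free T4 and ACTH if they are not graded.
- State that the worsening summary in SAP 7.6.2 uses the same full list.

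If the sponsor prefers the short list, SAP 4.1 should declare it with a reason, and 7.6.2 should say which tests it covers.

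The cost is programming of standard tables from data already collected, and more pages of output. The change does not add sampling, so tests in the full chemistry panel only, such as lipase, will still have no scheduled series during treatment cycles.
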